9.7.1. Descriptive Analysis

Dichotomous and categorical variables will be summarized by the number and percentage of patients in each category. Continuous variables will be described using mean (SD), median (IQR), minimum, and maximum. If applicable, the frequency and percentage of patients with missing data for each variable will be described. Missing categorical data will be included as a separate "missing" category. Missing continuous data will not be included in the summaries and analyses (i.e., only non-missing data will be analyzed). No imputations will be performed.

9.7.2. Treatment Exposure Outcomes

Treatment exposure outcomes include RAI and time between administrations. The assessment periods shown in Table 4 are based on the elranatamab label instructions and will be used to measure treatment and dosing-related outcomes for patients receiving elranatamab.¹⁹ The assessment periods shown in Table 5 are based on the teclistamab label instructions and will be used to measure treatment and dosing-related outcomes for patients receiving teclistamab.²⁰ These periods are also provided in Figure 2.

Table 4. Dosing Schedule and Expected Administrations and Vial Size of Elranatamab

Dosing Schedule	Dosing Schedule Time Period		Vial Size
Step-Up	Index date - Day 8	3	44mg/1.1mL, 76mg/1.9mL
Maintenance Period 1	Day 9 - Day 168	1 per week	76mg/1.9mL

[figure not shown]
Maintenance Period 2	Day 169 - Censor	1 every two weeks	76mg/1.9mL
----------------------	------------------	-------------------	------------

Table 5. Dosing Schedule and Expected Administrations and Vial Size of Teclistamab

[figure not shown]
Dosing Schedule	Time Period	Expected Administrations	Vial Size
Step-Up	Index date - Day 7	3	30 mg/3mL
Maintenance Period	Day 8 - Censor	1 per week	153 mg/1.7mL

Figure 2. Dosing Schedule for Elranatamab and Teclistamab

Elranatamab label instructions

Teclistamab label instructions

Dosing outcomes (reported vial size, average time between claims, and frequency of claims) will be assessed during the above time periods regardless of whether the number of administrations during the period matches the number indicated on the label instructions.

Patients will be censored at the earliest of death, next treatment (CAR-T, BsAbs, bendamustine or belantamab), the end of part A or B continuous closed-claim coverage, or the end of data.

9.7.3. Healthcare Resource Utilization and Cost

All-cause HCRU and MM-related HCRU (i.e., HCRU with a diagnosis code or treatment for MM) will be measured as the total number of per-patient-per-month (PPPM) IP, OP, ED, and pharmacy claims that occurred over the follow-up period. Medical claims will only be counted once per day to estimate visits. Additionally, the total length of IP stays will be reported among patients with at least one IP visit. Given the recency of the study period, costs will not be adjusted for inflation.

HCRU and costs will be measured across three different time periods: from the start of data to a day before the index date, from the index date until last recorded dose, and the time from discontinuation through the time of censoring. Patients will be censored at the earliest of death, next treatment (CART, BsABs, bendamustine or belantamab), the end of part A or B continuous closed-claim coverage, or the end of data.

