1	Talquetamab	Medical claim with an NDC, HCPCS, generic name or CPT code in the inpatient, non-IP, or pharmacy setting for talquetamab (dichotomous)	MM diagnosis to 1 day prior to index date
			Index date to the end of follow-up
1	PIs	Medical claim with an NDC, HCPCS, generic name or CPT code in the inpatient, non-IP, or pharmacy setting for bortezomib, carfilzomib, or ixazomib	MM diagnosis to 1 day prior to index date
		(dichotomous)	Index date to the end of follow-up
1	IMiDs	Medical claim with an NDC code or generic name in the non-IP or pharmacy setting for lenalidomide, thalidomide, or pomalidomide (dichotomous)	MM diagnosis to 1 day prior to index date
			Index date to the end of follow-up
1	Steroids	Medical claim with an NDC, HCPCS, generic name or CPT code in the inpatient, non-IP, or pharmacy setting for dexamethasone, methylprednisolone, prednisone, or prednisolone (dichotomous)	MM diagnosis to 1 day prior to index date
		prediffication, or prediffication (dieffotolificas)	Index date to the end of follow-up

Objective	Variable	Definition	Assessment Period(s)
1	mAbs	Medical claim with an NDC, HCPCS, generic name or CPT code in the inpatient, non-IP, or pharmacy setting for daratumumab, isatuximab, or elotuzumab (dichotomous)	MM diagnosis to 1 day prior to index date
			Index date to the end of follow-up
1	Chemotherapies	Medical claim with an NDC, HCPCS, generic name or CPT code in the inpatient, non-IP, or pharmacy setting for doxorubicin hydrochloride, melphalan, bendamustine, cyclophosphamide, etoposide, or	MM diagnosis to 1 day prior to index date
		cisplatin (dichotomous)	Index date to the end of follow-up
1	Small molecule inhibitors	Medical claim with an NDC, HCPCS, generic name or CPT code in the inpatient, non-IP, or pharmacy setting for venetoclax (dichotomous)	MM diagnosis to 1 day before index date
		setting for venerociax (dichotomous)	Index date to the end of follow-up
1	Nuclear export inhibitors	Medical claim with an NDC, HCPCS, generic name or CPT code in the inpatient, non-IP, or pharmacy setting for selinexor (dichotomous)	MM diagnosis to 1 day before index date
		coming for community (controlled as)	Index date to the end of follow-up
1	Antivirals	Medical claim with an NDC, HCPCS, generic name or CPT code in the inpatient, non-IP, or pharmacy setting for antiviral medications (dichotomous)	14 days prior to index date to 1 day prior to index date

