3	Total duration of all-cause IP stays	The total time in days of IP stays among patients who have at least 1 IP stay (continuous).	Start of data to 1 day before index date, index date until last recorded dose, and time from discontinuation through time of censoring
3	Total all-cause HCRU	IP, OP, ED, or pharmacy claims (dichotomous) Number of IP, OP, ED, or pharmacy claims	Start of data to 1 day before index date, index date until last recorded dose, and time from discontinuation through
3	MM-related IP visits	(continuous) Medical claim for IP (non-ED) visit with an MM ICD-10 code or treatment for MM (dichotomous) Number of IP (non-ED) visits with an MM	Start of data to 1 day before index date, index date until last recorded dose, and time from discontinuation through time of censoring
3	MM-related OP visits	ICD-10 code or treatment for MM (continuous) Medical claim for non-IP/non-ED visit with an MM ICD-10 code or treatment for MM (dichotomous)	Start of data to 1 day before index date, index date until last recorded dose, and time from
		Non-IP/non-ED visits with an MM ICD-10 code or treatment for MM (continuous)	discontinuation through time of censoring

	1		
3	MM-related pharmacy claims	Pharmacy claim with a treatment for MM (dichotomous)	Start of data to 1 day before index date, index date until last recorded dose, and time from
		Number of pharmacy claims with a treatment for MM (continuous)	discontinuation through time of censoring
3	Total duration of MM-related IP stays	The total time in days of IP stays with an MM ICD-10 code or treatment for MM, among patients who have at least 1 IP stay (continuous)	Start of data to 1 day before index date, index date until last recorded dose, and time from discontinuation through time of censoring
3	Total MM-related HCRU	IP, OP, ED, or pharmacy claims with an MM ICD-10 code or treatment for MM (dichotomous)	Start of data to 1 day before index date, index date until last recorded dose, and time from discontinuation through
		IP, OP, ED, or pharmacy claims with an MM ICD-10 code or treatment for MM (continuous)	time of censoring
3	Cost of all-cause IP visits	Cost of IP (non-ED) visits (continuous)	Start of data to 1 day before index date, index date until last recorded dose, and time from discontinuation through time of censoring

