Clinical events of interest defined by diagnosis codes may not capture the occurrence or intensity of the disease. Certain conditions, such as hematological toxicities, are often defined via specific cutoffs for certain lab values, which are not often provided in a claims data source. Therefore, ICD codes are used instead. Without lab values, the severity of the disease/grade cannot be determined. Therefore, patients whose adverse events were not as severe in grade may not be captured. Claims data do not contain variables used to assess standard oncology endpoints. Claims databases do not often detail clinical contexts, such as physician notes, imaging results, or laboratory findings. Common oncology endpoints such as real-world progression-free survival, real-world objective response rate, and reasons for discontinuation are typically defined using variables abstracted from patient charts that are not available in a claims dataset. Similarly, any treatments or drug utilization (such as over-the-counter purchasing of medications directly by patients) not directly reimbursed by the Medicare program will not be available for review.

The recency of elranatamab and teclistamab approval is important for interpreting results. The expected sample size is low, potentially resulting in uncertain estimates, as evidenced by wide confidence intervals. Very few eligibility criteria will be applied, which may allow patients with other malignancies or other conditions that are often excluded in a real-world study to enter. Additionally, the patients who have received elranatamab or teclistamab soon after approval may have more severe or advanced disease. Due to the recency of approval, the generalizability of outcomes may be limited to a brief period following initiation.

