			59572022016, 59572022096, 59572040200, 59572040228, 59572040528, 59572040500, 59572040528, 59572041000, 59572041028, 59572041500, 59572041521, 59572042501, 59572042501, 59572042501, 59572050200, 59572050221, 59572050300, 59572050221, 59572050300, 59572050321, 59572050400, 59572050421, 59651034201, 59651034207, 59651034228, 59651034201, 59651034207, 5965103428, 59651034401, 59651034407, 59651034428, 59651034501, 59651034407, 59651034421, 59651034501, 59651034507, 59651034521, 59651034601, 59651034607, 59651034521, 59651034601, 59651034607, 59651034721, 60505453202, 60505453301, 60505453302, 60505453401, 60505453501, 60505453502, 60505453602, 60505453701, 60505453702, 63304004101, 63304004127, 63304004201, 63304004227, 63304004401, 63304004227, 63304004401, 63304004422, 63304004501, 63304004422, 63304004401, 63304004422, 63304004501, 63304004522, 63304004601, 63304004522, 63304004601, 63304004522, 6300505453501, 70710103001, 70710103007, 70710103101, 70710103101, 70710103107, 70710103201, 70710103207, 70710103301, 70710103308, 70710103207, 70710103408, 70710103501, 70771167801, 70771167801, 70771167801, 70771167801, 70771167801, 70771167801, 70771168008, 70771168101, 70771168008, 70771168101, 70771168008, 70771168101, 70771168008, 70771168001, 70771168008, 70771168101, 70771168008, 70771168101, 70771168008, 70771168101, 70771168008, 70771168101, 70771168008, 70771168101, 70771168008, 70771168101, 70771168008, 70771168001, 70771168008, 70771168101, 70771168008, 70771168001, 70771168008, 70771168101, 70771168008, 70771168001, 70771168008, 70771168101, 70771168008, 70771168001, 70771168008, 70771168001, 70771168008, 70771168001, 70771168008, 70771168001, 70771168008, 70771168001, 70771168008, 70771168001, 70771168008, 70771168001, 70771168008, 70771168001, 70771168008, 70771168001, 70771168008, 70771168001, 70771168008, 70771168001, 70771168008, 70771168001, 70771168008, 70771168001, 70771168008, 70771168001, 70771168008, 70771168001, 70771168001, 70771168008, 70771168001, 70771168001, 70771168001, 70771168001, 7070
Steroids	Baseline	Claims	Pomalidomide HCPCS: C9034, C9256, J1020, J1030, J1040,
2.53.0.445	characteristic - Treatments, Outcome - HCRU	data	J1094, J1095, J1096, J1100, J2920, J2930, J7312, J7509, J7637, J7638, J8540, K0512, K0513, S0173, J7506, J7512 Generic names (and associated NDCs): Dexamethasone, Methylprednisolone,
			Prednisone, Prednisolone

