CD38 mAbs	Baseline characteristic - Treatments, Outcome - HCRU	Claims data	HCPCS: C9062, C9476, J9144, J9227, J9145 NDC: 00024065401, 00024065601, 57894050205, 57894050220, 57894050301, 57894050505, 57894050520 Generic names: Daratumumab, Isatuximab
mAbs	Baseline characteristic - Treatments,	Claims data	HCPCS: C9062, C9476, J9144, J9227, J9145, C9477, J9176

	0 :		NDC 00004065401 00004065601
	Outcome - HCRU		NDC: 00024065401, 00024065601, 57894050205, 57894050220, 57894050301, 57894050505, 57894050520, 00003229111, 00003452211
			Generic names: Daratumumab, Isatuximab, Elotuzumab
Chemotherapies	Baseline characteristic - Treatments, Outcome - HCRU	Claims data	HCPCS: C9080, C9087, C9243, C9420, C9421, J8530, J8600, J9033, J9034, J9036, J9056, J9058, J9059, J9070, J9071, J9080, J9090, J9091, J9092, J9093, J9094, J9095, J9096, J9097, J9245, J9246, J9247,
			J9000, C9415, J9002, Q2048, Q2049, Q2050, J9001, J9181, J9182, C9425, J8560, C9414, C9418, J9060, J9062
			Generic names (and associated NDC codes): Melphalan, Bendamustine, Cyclophosphamide, Doxorubicin, Etoposide, Cisplatin
Small molecule inhibitors	Baseline characteristic - Treatments, Outcome - HCRU	Claims data	NDC: 00074056111, 00074056114, 00074056607, 00074056611, 00074057611, 00074057622, 00074057630, 00074057634, 00074057928
	пско		Generic name: Venetoclax
Nuclear export inhibitors	Baseline characteristic - Treatments, Outcome - HCRU	Claims data	NDC: 72237010401, 72237010101, 72237010102, 72237010103, 72237010104, 72237010105, 72237010106, 72237010107, 72237010202, 72237010206, 72237010207, 72237010305
			Generic name: Selinexor
Antivirals	Baseline characteristic - Treatments	Claims data	HCPCS/CPT: J0133, Q4075, S0071, G9017, G9033, S0137, J1324, J1452, J1455, 67027, C9412, J1570, J1574, J7310, J1746, G9019, G9035, J2547, J0248, J0741, G9020, G9036, S0140, 0025U, G9018, G9034, J3485, S0104
			Generic names (and associated NDC codes): Abacavir, Acyclovir, Amantadine, Atazanavir, Baloxavir Marboxil, Bictegravir, Brivudin, Cobicistat, Daclatasvir, Darunavir, Delavirdine, Didanosine, Dolutegravir, Doravirine, Efavirenz, Elvitegravi, Emtricitabine, Enfuvirtide, Entecavir, Etravirine, Fameiclovir, Fomivirsen, Fosamprenavir, Foscarnet, Fostemsavir, Ganciclovir, Ibalizumab, Indinavir, Lamivudine, Ledipasvir, Lenacapavir, Letermovir, Lopinavir, Maraviroc, Maribavir, Molnupiravir, Nelfinavir,

			NT 1 NT 1 NT 1 NT 1 NT 1 NT 1

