Use of premedication	Outcome - Dosing and Administration Patterns	Claims data	HCPCS: J1094, J1096, J8540, J1100, J0131, J7637, J7638, J7312, J1200, Q0163 Generic names (and associated NDCs): Acetaminophen, Dexamethasone, Diphenhydramine
Inpatient	Baseline characteristic, Outcome - HCRU	Claims data	Any event in the inpatient table or an event in the non-inpatient table where acute_subacute is "acute inpatient" or where utilization type is "professional services", and service subcategory contains the term "hospital/IP encounter"
Outpatient	Baseline characteristic, Outcome - HCRU	Claims data	Any event in the non-inpatient table where utilization type is outpatient and service subcategory is not "emergency dept encounter"

Emergency department	Baseline characteristic, Outcome - HCRU	Claims data	Any event in the non-inpatient table where utilization type is "outpatient" and service subcategory is "emergency dept encounter"
Cytokine release syndrome (CRS)	Safety events	Claims data	ICD-10 Diagnosis: D89.83x
Immune effector cell- associated neurotoxicity Syndrome (ICANS)	Adverse events	Claims data	ICD-10 Diagnosis: G92.0x
Anemia	Adverse events	Claims data	ICD-10 Diagnosis: D46.0, D46.1, D46.20, D46.21, D46.22, D46.4, D46.9, D46.A, D46.B, D46.C, D46.Z, D47.4, D50.0, D50.1, D50.8, D50.9, D51.0, D51.1, D51.2, D51.3, D51.8, D51.9, D52.0, D52.1, D52.8, D52.9, D53.0, D53.1, D53.2, D53.8, D53.9, D55.0, D55.1, D55.2, D55.21, D55.29, D55.3, D55.8, D55.9, D59.0, D59.1, D59.10, D59.11, D59.12, D59.13, D59.19, D59.2, D59.3, D59.30, D59.31, D59.39, D59.4, D59.5, D59.6, D59.8, D59.9, D60.0, D60.1, D60.8, D60.9, D61.01, D61.09, D61.1, D61.2, D61.3, D61.810, D61.811, D61.818, D61.82, D61.89, D61.9, D63.0, D63.1, D63.8, D64.9, D75.81
Lymphopenia	Adverse events	Claims data	ICD-10 Diagnosis: D72.810
Hypogammaglobulinemia	Adverse events	Claims data	ICD-10 Diagnosis: D80.1, D80.3, D80.9
Hypophosphataemia	Adverse events	Claims data	ICD-10 Diagnosis: E83.39
Hypokalaemia	Adverse events	Claims data	ICD-10 Diagnosis: E87.6
Arthralgia	Adverse events	Claims data	ICD-10 Diagnosis: M25.5x
Pyrexia	Adverse events	Claims data	ICD-10 Diagnosis: R50.x
Hypotension	Adverse events	Claims data	ICD-10 Diagnosis: I95.0, I95.81, I95.89, I95.9, I95.2
Fatigue	Adverse events	Claims data	ICD-10 Diagnosis: R53.x, G93.3x

Nausea or vomiting	Adverse events	Claims data	ICD-10 Diagnosis: R11.x
Diarrhea	Adverse events	Claims data	ICD-10 Diagnosis: R19.7, K59.1

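### As coded in Annex 2, any steroid or non-specific chemotherapy claim can count as MM-related use and cost, whatever it was given for

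*Protocol*

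**What the plan says.** Section 9.7.3 splits resource use and cost into all-cause and MM-related, the latter being "MM-related HCRU (i.e., HCRU with a diagnosis code or treatment for MM". Table 3 repeats this either/or for inpatient and outpatient visits, inpatient days, totals and costs. For the number of pharmacy claims it drops the diagnosis and keeps only the drug: "Pharmacy claim with a treatment for MM (dichotomous".

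Neither place names the drugs. Table 3 refers to Annex 2 for codes, and Annex 2 has a role column:

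- The Steroids row has the role "characteristic - Treatments, Outcome - HCRU". It lists 21 HCPCS codes and then "Generic names (and associated NDCs): Dexamethasone, Methylprednisolone", followed by prednisone and prednisolone. Table 2 names the same four agents.
- The Chemotherapies row has the role "Baseline characteristic - Treatments, Outcome - HCRU" and covers melphalan, bendamustine, cyclophosphamide, doxorubicin, etoposide and cisplatin.
- Antivirals, antibiotics, antifungals and intravenous immunoglobulin have a baseline role only. Premedication has a separate dosing role.

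Section 9.9 states: "Very few eligibility criteria will be applied, which may allow patients with other malignancies". Section 9.7.3 starts the pre-index period at the start of data, which section 9.2 puts at 1 January 2016.

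**The concern.** Steroids and several of the listed chemotherapies are used for many diseases. If they count as MM treatment without any link to MM, the MM-related figures absorb care for other conditions. MM-related use and cost is half of primary Objective 3, and it is meant to separate myeloma care from everything else.

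Pharmacy claims are the most exposed, because their count depends on the drug list alone. Medical claims are exposed differently: one steroid or chemotherapy code can turn a whole visit or inpatient stay, with its cost, into an MM-related one.

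**Working it through.** The plan gives no figure for MM-related use or cost, so there is nothing to reproduce. The check follows the definition through the document.

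**1. The rule.** Section 9.7.3 and Table 3 join diagnosis and treatment by an or. Either is sufficient, so a claim without an MM code qualifies if the drug is on the list.

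**2. The list.** Annex 2 is the only code list. Its role column does discriminate: it gives the HCRU outcome to the myeloma drug classes, steroids and chemotherapies, and withholds it from anti-infectives, immunoglobulin and premedication.

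**3. Any restriction.** Section 9.7.3, Tables 2 and 3 and Annex 2 require no MM code on the same claim, no concurrent MM agent and no absence of another indication. Section 9.8 says the protocol's codes will be applied strictly.

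**4. Cases that follow.** Table 2 records chronic pulmonary disease, rheumatic disease and non-hematological malignancy at baseline, so the plan expects such patients.

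- Prednisone filled for lung or rheumatic disease: an MM-related pharmacy claim.
- A clinic or emergency visit with a methylprednisolone injection and no MM code: an MM-related visit and cost.
- Cisplatin for a second cancer: MM-related use and cost.

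**5. Timing.** Table 2 counts treatment history from MM diagnosis, but sections 9.7.3 and Table 3 count HCRU from the start of data. The same three claims would be MM-related even if they preceded the first MM diagnosis. Section 9.2 gives 180 days as the baseline HCRU window; under that window this part would disappear for anyone diagnosed more than 180 days before index.

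**6. Size, by assumption only.** Let *a* be true MM-related pharmacy claims per patient per month (PPPM) and *b* the non-MM steroid fills PPPM. The relative overstatement is *b/a*. Neither value is in the documents.

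- Cohort average, assuming 10% to 30% of patients have such fills at 0.5 to 1.0 per month: *b* = 0.10 × 0.5 = 0.05 to 0.30 × 1.0 = 0.30 PPPM.
- With *a* assumed between 0.5 and 2: from 0.05/2 = 2.5% to 0.30/0.5 = 60%.
- Single patient, assuming *b* of 0.1 to 1 and the same *a*: from 0.1/2 = 5% to 1/0.5 = 200%.

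No cost figure can be given, because the documents contain no prices.

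**The case against.** The best counter-argument is that no sentence says the role column defines MM treatment. The column is visibly imperfect, since the elranatamab and teclistamab rows carry only an inclusion role, and section 9.7 leaves detailed methods to a SAP. This stands as a caution: the link is an inference. It does not dispose of the point, because there is no other list and the protocol itself assigns these codes to the HCRU outcome.

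It is also fair that excluding all such drugs would lose genuine MM use, as every patient has an MM diagnosis. That is a reason to report both versions.

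Four stronger readings are tempting and are not supported:

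- A reader might infer that premedication is miscounted, since seven of the ten premedication codes ("HCPCS: J1094, J1096, J8540, J1100, J0131, J7637, J7638, J7312, J1200, Q0163") are also in the Steroids row. Premedication accompanies the MM drug, that visit would normally be MM-related anyway, and medical claims count once per day. The overlap is not a measure of error.
- A reader might infer that the index drugs' own claims fall outside MM-related use. Section 8 describes elranatamab as a treatment of MM, so this is a labelling gap.
- A reader might infer that MM-related pharmacy counts would mostly reflect steroid fills. The same list includes immunomodulatory drugs, ixazomib, selinexor and venetoclax, and no rates are given.
- A reader might infer that entitlement subgroups or drug cohorts are distorted to different degrees. Nothing in the documents shows different non-MM steroid use. The definition is common to both cohorts, results are reported separately, and no formal comparison is planned.

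**Conclusion.** The point holds as a defect of definition. With Annex 2 read through its role column, the plan labels steroid and non-specific chemotherapy claims as MM-related without any connection to MM, and under the section 9.7.3 window it does so even before the first MM diagnosis. Section 9.9 discusses other misclassification but not this one.

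MM-related counts could be inflated. Costs could be too, to an unknown extent that is probably smaller for low-priced oral steroids. The percentages above illustrate assumed rates and are not estimates. The conclusion rests on the role column being the operative list. All-cause results are unaffected.

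**What to change.** In section 9.7.3, Table 3 and Annex 2:

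1. State which rows make a claim MM-related on their own, and limit these to MM-directed agents. Add the HCRU role to the elranatamab and teclistamab rows. Say on which side melphalan, bendamustine and venetoclax fall.
2. Count a medical claim with a steroid or non-specific chemotherapy as MM-related only if it carries C90.0x.
3. Count no claim as MM-related on treatment alone before the first MM diagnosis.
4. Report MM-related pharmacy claims and costs both with and without steroids and non-specific agents.

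The cost is a change of code roles, one extra table row and possibly a rerun of interim code, since the December 2024 and June 2025 deliveries were scheduled before this version; the final analysis is planned for February 2026. Some genuine MM steroid or chemotherapy use would appear only in the broader row.

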9.2. Setting

This study will evaluate adult patients with RRMM who initiate elranatamab or teclistamab. Patients will enter (i.e., index) on the first observed elranatamab or teclistamab claim between August 14, 2023 and March 2025. Limited eligibility criteria will be applied.

Study Period: Start of data (Jan 1, 2016) to the most current, available data.

MM diagnosis window: Start of data (Jan 1, 2016) to index date

Index date: First elranatamab or teclistamab claim after initial MM diagnosis

Observability: At least 180 days of continuous closed-claims medical and pharmacy enrollment prior to index (inclusive) and 30 days after the index date

Baseline period for MM-related treatments and MM-related comorbidities: MM diagnosis to one day prior to index date

Charlson Comorbidity Index and baseline HCRU assessment window: 180 days prior to index date to index date

Follow-up: Index date until death, the earliest of end of study period, or end of continuous enrollment (unless otherwise noted). Alternative censoring criteria will be applied for certain outcomes (such as OS, TTD, and TTNT/D).

Figure 1 reflects the time periods of interest in the study cohort. The data end date in Figure 1 will be updated at the time of the second, third, and final analyses, estimating data through June, September, and December 2025, respectively. All other dates shown in the figure will remain the same for the subsequent analyses.

[figure not shown]

Figure 1. Study Schematic for Patients Receiving Elranatamab or Teclistamab

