2	Average time between elranatamab or teclistamab claims	Sum of the days between claims for the index drug (continuous) divided by the total number of administrations -1	Index date to the end of follow-up Step-Up Dosing Period

	1	T	T
			Maintenance Periods
2	Frequency of elranatamab or	Total number of inpatient, non-IP, and pharmacy claims of the index drug during the	Index date to the end of follow-up
	teclistamab claims	time period based on vial size (continuous)	Step-Up Dosing Period
			Maintenance Periods
2	Relative Administration Intensity (RAI)	The ratio of the actual administrations received divided by the expected number of administrations according to the US label	Index date to the end of follow-up
		(continuous)	Step-Up Dosing Period
			Maintenance Periods
2	Time to Discontinuation (TTD)	Time in months from first administration until last administration prior to treatment discontinuation (continuous). Treatment discontinuation is defined as an 8-week gap in elranatamab or teclistamab therapy, next treatment after index treatment (CAR-T, BsABs, bendamustine or belantamab), or death.	Index date to the end of follow-up
2	Reason for Discontinuation	Reason for treatment discontinuation used to estimate time to discontinuation, either an 8-week gap in elranatamab or teclistamab therapy, next treatment after index treatment (CAR-T, BsABs, bendamustine or belantamab), or death.	Index date to the end of follow-up
Health care	resource utilization an	d costs	
3	All-cause IP visits	Medical claim for IP (non-emergency department [ED]) visit (dichotomous)	Start of data to 1 day before index date, index date until last recorded dose, and time from discontinuation through time of censoring
		Number of IP (non-ED) visits (continuous)	
3	All-cause OP visits	Medical claim for non-IP/non-ED visit (dichotomous)	Start of data to 1 day before index date, index date until last recorded dose, and time from
		Number of non-IP/non-ED visits (continuous)	discontinuation through time of censoring

3	All-cause ED visits	Medical claim for ED visit (dichotomous) Number of ED visits (continuous)	Start of data to 1 day before index date, index date until last recorded dose, and time from discontinuation through time of censoring
3	All-cause pharmacy claims	Pharmacy claim (dichotomous) Number of pharmacy claims (continuous)	Start of data to 1 day before index date, index date until last recorded dose, and time from discontinuation through time of censoring

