9.7. Data Analysis

This study will be largely descriptive in nature, and no formal statistical comparisons will be performed between groups. All characteristics and outcomes will be reported separately for each cohort. The number of patients who meet study eligibility criteria will be summarized in an attrition table. Inclusion and exclusion criteria will be listed hierarchically and the number of patients remaining at each step will be reported. Patient and treatment characteristics will be summarized using descriptive statistics. Categorical variables will be summarized by the number of available observations, frequency, percentage, and 95% confidence limits. Continuous variables will be summarized by the number of available observations, mean, standard deviation, 95% confidence limits, median, quartiles, minimum, and maximum, where appropriate. The prevalence and incidence, as well as the associated 95% confidence intervals (CI) for each adverse event, will be estimated. Kaplan-Meier methods will be used to estimate the median time to event, including 95% CIs for TTNT/D and OS. All-cause HCRU and MM-related HCRU will be measured as the mean, SD, median, IQR, minimum, and maximum of the total number of IP, OP, ED, and pharmacy claims. Given the variable follow-up time available for each patient, HCRU and costs will be reported, for instance, on a per-patient-per-month (PPPM) basis. Relative Administration Intensity (RAI) will be calculated as the ratio of the actual number of administrations during each time period divided by the expected number of administrations based on the label for the treatment.

Based on the study cohorts of interest, patients may be characterized by the following attributes of interest:

- Demographic characteristics such as age, sex, race/ethnicity, state, and region
- Reason for Medicare enrollment
- Social determinants of health such as household income, education level, marital status, and home ownership

PFIZER CONFIDENTIAL

- Clinical characteristics such as comorbidity and past treatment status
- Healthcare resource utilization such as hospitalization and place of service distribution

Subgroup analysis will identify samples of patients based on reason for Medicare entitlement: disabled beneficiaries, beneficiaries with end-stage renal disease (ESRD), and beneficiaries aged 65 to 115 years qualifying by age.

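### Pre-index HCRU and cost are measured from 1 January 2016 in Section 9.7.3 and Table 3, against a 180-day baseline window in Section 9.2 and only 180 days of guaranteed enrolment

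*Protocol*

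**What the plan says.** Two windows are given for resource use before index.

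- **Long window.** Section 9.7.3 sets the first of its three HCRU and cost periods as "from the start of data to a day before the index date". The HCRU and cost rows of Table 3 (Section 9.3) repeat it: "Start of data to 1 day before index date, index date until last recorded dose, and time from discontinuation through time of censoring". Section 9.2 dates the start: "Study Period: Start of data (Jan 1, 2016) to the most current, available data".
- **Short window.** Section 9.2 also states: "Charlson Comorbidity Index and baseline HCRU assessment window: 180 days prior to index date to index date".

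The enrolment requirement in Section 9.2 is "At least 180 days of continuous closed-claims medical and pharmacy enrollment prior to index (inclusive) and 30 days after the index date". Section 9.2 places index dates "between August 14, 2023 and March 2025".

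On scale, Section 9.7 says: "Given the variable follow-up time available for each patient, HCRU and costs will be reported, for instance, on a per-patient-per-month (PPPM) basis". Section 9.7.3 describes PPPM claims over follow-up, which Section 9.2 starts at index. No denominator is given for the pre-index period.

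**The concern.** Objective 3, a primary objective, is to describe HCRU and cost. The two windows differ by a factor of more than 15, so a programmer following Section 9.2 and one following Section 9.7.3 would produce different baseline tables.

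The long window is also weak in itself. The coverage rule in Section 9.7.3 is a censoring rule that ends follow-up. Nothing makes the pre-index window begin when a patient becomes observable or when MM is first diagnosed. By contrast, Section 9.2 starts the baseline period for MM treatments and MM comorbidities at MM diagnosis. At stake is whether the pre-index columns describe patients' use of care or merely how long each patient has been visible in Medicare claims.

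A side effect concerns cost. Section 9.7.3 forgoes inflation adjustment because the study period is recent, which does not fit costs reaching back to 2016.

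**Working it through.** The protocol states no figure to reproduce here. The check is date arithmetic and a comparison of passages.

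**Inputs**
- Start of data: 1 January 2016 (Section 9.2).
- Index dates: 14 August 2023 to March 2025 (Section 9.2), taking 31 March 2025 as the last day. Section 9.2.1 allows index dates up to the latest available data; later dates only lengthen the window.
- Guaranteed enrolment before index: 180 days (Sections 9.2 and 9.2.1, Table 1).
- Month length: 30.4375 days, as Section 9.7.5 uses for time to discontinuation.

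**Step 1. Length of the long window** (index date minus start of data)
- Earliest index: 2,782 days; 2,782 / 30.4375 = 91.4 months.
- Latest index: 3,377 days; 3,377 / 30.4375 = 110.9 months.

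**Step 2. Compared with guaranteed enrolment**
- 180 / 30.4375 = 5.9 months.
- 2,782 / 180 = 15.5 and 3,377 / 180 = 18.8.
- Guaranteed enrolment therefore covers 180 / 2,782 = 6.5% to 180 / 3,377 = 5.3% of the window.

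**Step 3. Who has unobservable time**
- The window spans 2,782 / 365.25 = 7.6 to 3,377 / 365.25 = 9.2 years.
- Section 9.7 identifies a subgroup entitled by age, from 65 years. A patient entitled only by age and younger than about 65 + 7.6 = 72.6 years (earliest index) or 65 + 9.2 = 74.2 years (latest index) was not yet 65 on 1 January 2016. Part of that patient's window precedes entitlement.
- Beneficiaries entitled through disability or end-stage renal disease may also have entered after 2016.
- The Medicare Advantage exclusion (Section 9.2.2) removes gaps from that source, but not time before entitlement.

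**Step 4. Measures affected whatever the denominator**
- Table 3 includes yes/no use, visit counts and total inpatient days. These grow with observable time, which can run from 180 days to over nine years, and the post-index periods are of different length again.
- MM-related use needs an MM code or an MM treatment. Before the first MM code only treatments that also have other uses, such as steroids, can register. Hence it is near zero rather than exactly zero.

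**Step 5. PPPM, if calendar months were the denominator** (an assumption; the protocol does not say so)

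Apparent rate / rate in enrolled time = enrolled months / window months.

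| Enrolled months before index | Index 14 Aug 2023 | Index 31 Mar 2025 |
|---|---|---|
| 5.9 (180 days) | 5.9 / 91.4 = 6.5% | 5.9 / 110.9 = 5.3% |
| 24 | 24 / 91.4 = 26% | 24 / 110.9 = 22% |
| 60 | 60 / 91.4 = 66% | 60 / 110.9 = 54% |
| Whole window | 100% | 100% |

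With enrolled months as the denominator, every cell is 100%.

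**The case against.** **The denominator is a matter for the statistical analysis plan.** PPPM is offered only as an example and is tied to follow-up. Section 9.6 says the analytic file holds enrolment dates, so enrolled months can be computed, and Section 9.7 leaves detailed methods to the separate plan. This stands. A reader might infer that months without Medicare will be counted as zero-use months, and that baseline PPPM will be diluted up to 18.8-fold. The protocol neither says this nor rules it out. It does state two different windows, and that is more than an omitted detail. Section 9.8 promises strict adherence to the protocol, and Section 9.7 says major changes to primary endpoint definitions would be reflected in an amendment.

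**No before-and-after contrast is planned.** Objective 3 is descriptive and Section 9.7 rules out formal comparisons between groups. A reader might infer that the rise in use after index will be overstated. The documents do not support this: no rise is stated, and the direction is not uniform. A calendar denominator would lower pre-index PPPM, while the long window raises pre-index any-visit proportions and total inpatient days.

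**Months before myeloma are not empty.** For all-cause measures, enrolled months before MM carry ordinary claims and costs. The problem there is that pre-disease use is mixed into the baseline. Only MM-related measures are near zero.

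**The two windows might serve different purposes.** Annex 2 lists inpatient, outpatient and emergency visits both as baseline characteristics and as outcomes. But Table 2, which holds the baseline variables, has no HCRU row, so no listed variable uses the 180-day HCRU window. Even on this reading the long window remains untied to enrolment.

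**Many patients may be fully enrolled.** Section 9.9 expects an older sample, and the documents give no enrolment distribution. The 180-day patient is therefore the extreme case.

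**Conclusion.** The point holds as a contradiction on a primary objective combined with a poorly bounded window. Section 9.7.3 and Table 3 look back 91.4 to 110.9 months, Section 9.2 looks back 180 days, and only the latter is covered by the enrolment requirement. Under the long window, counts, any-visit proportions and total inpatient days are not comparable between patients or with the post-index periods. This needs no assumption about PPPM.

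The effect on PPPM is conditional. With calendar months it runs from nil for a patient enrolled since 2016 to 15.5- to 18.8-fold for a patient with exactly 180 enrolled days; with enrolled months there is none. How many patients lie near either end cannot be read from the protocol.

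**What to change.** 1. In Section 9.7.3 and every HCRU and cost row of Table 3, define the pre-index period as the 180 days before index, Day -180 to Day -1.
2. In Section 9.2, end the baseline HCRU window the day before index. It now includes the index date, on which the on-treatment period also starts, so the two would overlap.
3. If a longer history is wanted, report it as a second, separate window restricted to continuously enrolled time, with enrolled person-months as the denominator. For MM-related measures, start it no earlier than first MM diagnosis.

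The main window then holds less pre-index history, and several table rows need editing. The optional second window needs some enrolment logic. No new data are required, since Section 9.6 already places enrolment dates in the analytic file.
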